4. Extraoral Photos

For the same subset of subjects, a final photo will be taken after whitening is completed, using the same techniques as before (with retractor in place, and no gingival barrier).

5. Questionnaire

Subject and provider will complete the relevant portions of a short questionnaire.

6. Study Product Distribution:

All subjects enrolled in the study will be provided with a soft-bristled adult toothbrush and toothpaste for home use. Subjects will be instructed to brush their teeth twice daily (morning and evening) for two (2) minutes each time with the toothpaste and toothbrush provided. All subjects will be instructed to repeat the same procedure twice daily for the duration of this study.

7. Instruction to Subjects

Subjects will be instructed to use only the products (toothpaste and toothbrush) provided during the study period, and to refrain from using any other oral hygiene products and from routine dental treatment (except emergency) during the course of the study. Subjects who receive dental treatment and/or use medication must report this to the study investigators. The use of tooth whitening products is prohibited. There will be no restrictions regarding diet during the course of the study. Subjects will be asked to return to the clinical facility 1 week post-treatment for subsequent clinical examinations.

Example of Label Instruction for both test and control groups (Appendix XI):

CRO-2025-09-WHT-MS

Product (Letter Code)

Brush your teeth twice daily (morning and evening) for two (2) minutes each time. Cover the entire length of the bristled head with toothpaste. Do not swallow. For investigational use only by the study participant. Not for Retail Sale. For Adult Use Only. Keep out of reach of children under 6 years.

In case of emergency or for further information telephone:

[name] at [contact]

Visits 2: (7 days +/- 3 days after Baseline):

1. Visit Form

After 7 days of study product use at home, all subjects will report back to the clinical site for their follow-up appointment. The study examiner will complete a Study Visit Form (Appendix IX) to account for health updates and/or adverse reactions.

2. Subsequent Oral Soft and Hard Tissue Assessment

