Study products will be supplied by the sponsor for this study. The study investigator will verify that the quantity of supplies, protocol number, and identification numbers match the information on the shipping invoice, and will store and account for the study supplies as described below.

Study Products Storage, Handling, and Accountability

The study products must be stored in a secure area with limited access, at room temperature. The investigator is directly responsible for the accountability of all used and unused study products. The investigator and all sub-investigators will make every effort to remain blinded as to the subject regimen. Records must be maintained to document the receipt and disposition of all study drug supplies provided to the investigator by the sponsor. The study monitor will review these records periodically during the course of the study. At the end of the study, or as directed by the monitor, the investigator must return all unused study products to the sponsor.

XIV. CONCOMITANT THERAPY

If a subject takes concomitant medications as a matter of necessity for the treatment of a medical condition, then such medication may be permitted for the duration of the study at the discretion of the investigator. However, it is the responsibility of the investigator to disqualify from entering the study any subject who, upon screening, is using medication or consumer products that might obscure the interpretation of study results. All medications currently used by the subject at enrollment, or any time through the end of the study, will be recorded on medical history and visit form. Subjects may receive medication to treat adverse events as deemed necessary by the investigator or the subject's physician.

XV. ADVERSE EVENTS

A. DEFINITIONS:

Adverse Events (AEs) and Serious Adverse Events (SAEs) are defined by the ICH Guideline for Good Clinical Practice (ICH GCP) as follows:

U.S. 1R8

Adverse Event: Any untoward medical occurrence in a patient or clinical investigations subject administered a pharmaceutical product and which does not necessarily have to have a causal relationship with this treatment. An adverse event (AE) can therefore be any unfavorable and unintended sign (including abnormal laboratory finding), symptom, or disease temporally associated with the use of a medicinal product, whether or not considered related to the medicinal product.

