Study Originator (SO) receives the Form 105361 Adverse Event/Reaction Reporting Form for Non-Interventional Studies from the investigator for non-serious AER within one (1) calendar day (no later than 1 business day) of investigator awareness and forwards to [contact] and [contact] within one (1) calendar day (no later than 1 business day) upon receipt from investigator.

End of Study Reporting

Within 2 weeks of study completion the SO must complete Form 105362 Periodic/End of Study Report Form for Non-Interventional Studies on Humans documenting adverse event/reaction information reported during conduct of the study and submits it to [contact] and [contact].

XVI. PREGNANCY

No self-reported pregnant women will be enrolled in this study. In the event a woman enrolled in this clinical research study becomes pregnant during the course of the study, participation in this study will be terminated upon the clinical staff's notification of the event. The subject's medical records used in this study will be updated to reflect the pregnancy and there will be follow-up contact until the end of the pregnancy to record the outcome in the clinical file.

XVII. SUBJECT TERMINATION/WITHDRAWAL PROCEDURES

A genuine effort will be made to determine the reason(s) why a subject fails to return for the necessary visit(s) or is dropped from the study. Subjects could be dropped from the study if any of the following occur:

- 1. Subject fails to substantially comply with the protocol requirements.
- 2. Subject fails to report for a scheduled examination.
 - 3. Subject is treated with medication(s) during the course of the study, which may interfere with the parameters under study.
- 4. Subject receives emergency dental or medical treatment, which may interfere with the parameters under study.
- 5. Subject develops a serious adverse reaction. The Study Investigator will immediately notify the study monitor and information will be recorded on an Adverse Reaction Form (Appendix X).
- 6. Sponsor elects to terminate the study.
- 7. Subject elects to terminate participation in the study.

A study Visit Form (Appendix IX) indicating end of study participation must be completed for all subjects entered into the study even if they do not complete the study.

XVIII. NEW FINDINGS

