- Push the contents of the clear plunger completely back into the red syringe.
- To thoroughly mix, continually push the stems back and forth, mixing 25 times each side.
- Push all mixed gel into the red syringe.
- Twist to separate the two syringes and securely attach the recommended tip (Black Mini tip) onto the red syringe.
- o Verify gel flow, consistency, and ensure the gel is red before applying intraorally. If resistance is met or the gel is not red, do not use and re-check mixing steps.
- o Note: Opalescence Boost 40% should be used within 10 days of mixing. Keep refrigerated between uses.

II. In-Office Whitening Treatment

1. Isolation (OpalDam™ Resin Barrier - Recommended):

- o Remove Luer lock cap from the OpalDam resin barrier and securely attach the recommended delivery tip.
- Verify flow prior to applying intraorally.
- Rinse and dry teeth and gums thoroughly.
- Place Ultradent IsoBlockTM bite block and self-supporting lip/cheek retractors (or Ultradent Umbrella™ retractor) to avoid contact with soft tissue.
- Apply OpalDam resin barrier along the gingival margin, overlapping approximately 2-3mm onto the enamel. Begin and finish one tooth beyond the most distal tooth being whitened.
- o Express resin through any open embrasures onto the lingual tissue to completely seal and cover exposed papilla.
- Use a mouth mirror to ensure no gaps exposing underlying gingiva; apply resin to any
- o Light cure OpalDam for 20 seconds per arch using a scanning motion. When isolating a single tooth, scan for 5 seconds. Carefully check resin cure with an instrument.

OCT - 7 2025

O Note: If improper soft tissue isolation leaves patient's soft tissue exposed to peroxide gel, immediately wipe the gel from the tissue, rinse the area well. Tissue should return to normal within 20-30 minutes. If chemical irritation occurs, administer a nonsteroidal antiinflammatory drug (NSAID) as per instructions.

2. Isolation (Rubber Dam - Alternative):

o Place rubber dam to isolate the teeth being whitened.

3. Eye Protection:

o Patient and dental professional must wear protective eyewear with side shields when handling the product.

4. Whitening Gel Application:

- Apply a 0.5-1.0mm thick layer of the mixed red gel to the labial surface of the tooth/teeth to be whitened.
- o Allow gel to remain on the teeth for 20 minutes per application, periodically checking patient comfort and suctioning saliva.

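### Section XVII allows subjects to be dropped after the only whitening treatment without requiring their Day 7 assessments, so Day 7 data may be missing for reasons linked to tolerability

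*Combined protocol and SAP*

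**What the plan says.** Sections III and V describe one in-office whitening treatment at Visit 1. Shade and tissue examinations follow immediately (Visit 1b) and again at Visit 2, 7 days later with a window of 3 days either side. Between the visits subjects use only the supplied toothpaste and toothbrush.

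Section XVII states: "Subjects could be dropped from the study if any of the following occur". Seven reasons follow. Items 1 and 2 are substantial non-compliance and a missed examination. Item 3 reads "Subject is treated with medication(s) during the course of the study, which may interfere with the parameters under study". Item 4 reads "Subject receives emergency dental or medical treatment, which may interfere with the parameters under study". Item 5 begins "Subject develops a serious adverse reaction" and adds notification of the study monitor and an Adverse Reaction Form. Items 6 and 7 are termination by the sponsor and withdrawal by the subject.

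For those who leave, Section XVII requires a Visit Form "indicating end of study participation must be completed for all subjects entered into the study even if they do not complete the study". Section V (Visit 2) and Section VI repeat the form requirement for non-completers. No section says that a dropped subject is still asked for the Day 7 shade reading, tissue examination or questionnaire.

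Other sections allow or direct care that could fall under item 3. Section XIV says "Subjects may receive medication to treat adverse events as deemed necessary by the investigator" or by the subject's physician. In Appendix XII, a note in the Opalescence isolation step begins "If chemical irritation occurs, administer a" and goes on to name a non-steroidal anti-inflammatory drug.

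**The concern.** In a trial with continuing treatment, a discontinuation list can serve to stop exposure. Here the whitening is complete before a post-treatment trigger arises, so removing the subject from the study gives up the follow-up observation and nothing else. Section XVII does not separate stopping a product from ending data collection.

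Some triggers can follow from how the treatment was tolerated. Tolerability may differ between a 40% gel, a 25% gel with a lamp and a 25% gel with an LED tray, and gel exposure may affect both tolerability and whitening. If subjects are dropped on that path, the Day 7 comparison drifts from all randomised and treated subjects towards those who tolerated treatment and stayed. Section VII promises treatment comparisons at all time points but gives no analysis set or missing-data rule to cover the gap.

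Two safety items would go with the visit: the Day 7 tissue examination, whose new abnormal findings Section V turns into adverse events, and the prolonged-sensitivity question, which Appendix XIII asks only at one week.

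**Working it through.** **The plan's own figure.** Section II gives 180 subjects and about 10% drop-out. 180 x 0.10 = 18 lost and 180 - 18 = 162 completing, or about 6 lost and 54 completing per arm of 60. Section II's figure of eighteen completers matches the number lost, not the number completing. That is a separate slip and does not affect this point. The 10% is not split by cause or by arm.

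**Which triggers can fall after whitening, and what is then required**

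| Section XVII item | Qualifier | Required record |
|---|---|---|
| 1 Non-compliance | Substantial | Visit Form |
| 2 Missed examination | None | Visit Form |
| 3 Medication | May interfere with study parameters | Visit Form |
| 4 Emergency treatment | May interfere with study parameters | Visit Form |
| 5 Adverse reaction | Serious only | Visit Form and Adverse Reaction Form |

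The protocol does not define interference with the parameters under study. Its opening pages list tissue assessment and safety as endpoints beside whitening, so a site could read item 3 as covering medication for gingival irritation.

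The order of work at Visit 2 matters too. The Visit Form comes first, then the tissue examination, brushing and shade reading. The form asks whether the subject will continue, so a subject who attends and reports a medication could be dropped before being examined.

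**Formula.** Let p be the share of an arm dropped and D the mean shade change of the dropped minus that of the retained. The observed mean of that arm is off by p x D in size. The arm difference is off by p1 x D1 - p2 x D2, which is zero when p and D are equal in the two arms.

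**In tabs, with assumed inputs.** Take 10 of 60 dropped in one arm, 2 of 60 in another, and the same D in both. The two arms together lose 12 of 120, or 10%.
- D = 1: 10/60 x 1 - 2/60 x 1 = 0.13 tabs
- D = 2: 0.333 - 0.067 = 0.27 tabs
- D = 3: 0.500 - 0.100 = 0.40 tabs

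**In SD units, with assumed inputs.** The documents give no SD. With D from 0.25 to 1.0 SD, the same in both arms, and a two-sided 0.05 test by normal approximation, the standard error is sqrt(1/n1 + 1/n2), with n the number retained out of 60.

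| Loss, arm 1 vs arm 2 | Bias (SD) | Type I error |
|---|---|---|
| 10% vs 10% | 0 | 5.0% |
| 5% vs 15% | 0.025 to 0.10 | 5.2% to 8.1% |
| 0% vs 10% | 0.025 to 0.10 | 5.2% to 8.3% |
| 0% vs 20% | 0.05 to 0.20 | 5.8% to 17.8% |

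Example, 0% vs 10% with D = 1: the standard error is sqrt(1/60 + 1/54) = 0.188, and a bias of 0.10 gives 8.3%.

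**Gain in precision from full follow-up.** The difference detectable with 80% power is (1.960 + 0.842) x sqrt(2/n). It is 0.54 SD at n = 54 and 0.51 SD at n = 60. The benefit is less selection; the gain in power is small.

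**The case against.** A reader might infer that any reaction leads to removal and that Day 7 data are therefore lost in the subjects who tolerated treatment worst. The documents do not support this. The rule is permissive, item 5 covers only serious reactions as Section XV defines them, and items 3 and 4 apply only to care that may interfere with the study parameters. Ordinary sensitivity or gum irritation is not a trigger in itself, and nothing shows that the anti-inflammatory in Appendix XII would count as interfering. This part of the objection stands in full.

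A reader might also infer that safety will look better than it was. Section XV has the investigator follow every adverse event until it resolves or is no longer of clinical concern, with no exception for dropped subjects. Section VII lists and tabulates discontinuations due to adverse events. Visit 1b shade, tissue and sensitivity data precede any later drop. What remains is narrower: follow-up covers events already known, while an examination that is not done cannot find a new one.

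Finally, Section V expects all subjects back at Day 7, and no contact is scheduled in between. Most medication or dental treatment would thus come to light with the subject already at the clinic, where the Visit Form's question on exclusion from analysis may be the more direct risk. That is fair, but it is a separate matter. It does not remove the permission to drop the subject, and the form is completed before the examinations.

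**Conclusion.** The point holds as a gap that should be closed. Section XVII permits dropping after the only whitening treatment, and nothing in the protocol asks dropped subjects for Day 7 shade, tissue and questionnaire data. Those data may therefore go uncollected, for reasons that may relate to tolerability and may differ between arms.

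The size and direction of any bias cannot be derived from the documents. The 0.13 to 0.40 tabs and 0.025 to 0.20 SD above rest wholly on assumed loss rates and assumed D, and should not be read as estimates. Some of the expected 10% loss, such as withdrawal by choice or a missed appointment, need not involve tolerability at all. Safety information is reduced, not wholly lost.

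**What to change.** Amend Section XVII so that items 1 to 5, when they occur after whitening, do not by themselves end data collection. State that:
- every treated subject who has not withdrawn consent is asked to attend Visit 2 (7 days, plus or minus 3) for the shade reading, tissue examination and questionnaire;
- the medication, treatment or deviation is recorded;
- a missed visit is rebooked within the window before the subject is counted as lost.

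The pregnancy rule in Section XVI and decisions on use of the supplied products are not part of this change and stay as they are.

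The cost is amendment wording and a few more attended visits, all already scheduled. The downside is that a few Day 7 readings will follow a medication or dental treatment, which will be on record.

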APPENDIX I Tooth Shade Assessment Guidelines

Room and Lighting Conditions

- Assessments are conducted in a windowless room with the door closed to control ambient light.
- Only color-corrected overhead lighting between 5500-6500 Kelvin is used, simulating natural daylight. No operatory lights are used.

Subject Preparation

- On-site, supervised brushing with assigned product prior to clinical examinations.
- Subjects wear a blue or gray bib to neutralize clothing color influence.
- All makeup, hats, jewelry, and accessories are removed to avoid interference with shade selection.

Positioning

- Chair height and subject position are adjusted to provide a direct, shadow-free view of maxillary anterior teeth.
- All examinations are performed with the subject in the same position for consistency.
- Subjects are instructed to smile without showing their tongue.

Assessment Procedure

- A single, trained, and calibrated examiner (dentist) conducts all assessments.
- The examiner focuses on the facial (middle third) area of the tooth.
- The shade matching tab is held adjacent to the subject's tooth during assessment for comparison.

Visual Fatigue Management

- The examiner waits at least 5 minutes between assessments, resting their eyes on a blue background to prevent visual fatigue, for consistent and reliable tooth shade assessments.

APPENDIX V

SAMPLE OF HEALTH QUESTIONNAIRE

Date of Birth:	Race: Smoker: [] Yes [] No
	MEDICAL HISTORY
Name of Physician	
Name of Filysician.	Phone#:
Date of last visit:	Emergency contact? Name:
Phone #:	Your current physical health is: GoodFairPoor
Have you ever had any serio	ous operations? [] Yes [] No
If yes, please explain:	
Are you currently under the	care of a physician? [] Yes [] No
,	
	[] Tes[] No
If yes, Please explain:	
If yes, Please explain:	een treated for or told that you have:
If yes, Please explain: Please check if you have b [] Abnormal bleeding	een treated for or told that you have: [] Anemia
If yes, Please explain: Please check if you have b [] Abnormal bleeding [] Hemophilia	een treated for or told that you have: [] Anemia [] AIDS
If yes, Please explain: Please check if you have b [] Abnormal bleeding [] Hemophilia [] Blood transfusion	een treated for or told that you have: [] Anemia [] AIDS [] Arthritis
If yes, Please explain: Please check if you have b [] Abnormal bleeding [] Hemophilia [] Blood transfusion [] Ulcers/Colitis	een treated for or told that you have: [] Anemia [] AIDS [] Arthritis [] Glaucoma
If yes, Please explain: Please check if you have b [] Abnormal bleeding [] Hemophilia [] Blood transfusion [] Ulcers/Colitis [] Heart problems [] Epilensy/Soizuros	een treated for or told that you have: [] Anemia [] AIDS [] Arthritis [] Glaucoma [] Drug addiction
If yes, Please explain: Please check if you have b [] Abnormal bleeding [] Hemophilia [] Blood transfusion [] Ulcers/Colitis [] Heart problems [] Epilepsy/Seizures	een treated for or told that you have: [] Anemia [] AIDS [] Arthritis [] Glaucoma [] Drug addiction [] Skin problems
If yes, Please explain: Please check if you have b [] Abnormal bleeding [] Hemophilia [] Blood transfusion [] Ulcers/Colitis [] Heart problems [] Epilensy/Soizuros	een treated for or told that you have: [] Anemia [] AIDS [] Arthritis [] Glaucoma [] Drug addiction [] Skin problems [] Blood Disorders
If yes, Please explain: Please check if you have b [] Abnormal bleeding [] Hemophilia [] Blood transfusion [] Ulcers/Colitis [] Heart problems [] Epilepsy/Seizures [] Asthma or Hay fever [] Chemo/Radiation therage	een treated for or told that you have: [] Anemia [] AIDS [] Arthritis [] Glaucoma [] Drug addiction [] Skin problems [] Blood Disorders Oy [] Cancer/Tumor
If yes, Please explain: Please check if you have b [] Abnormal bleeding [] Hemophilia [] Blood transfusion [] Ulcers/Colitis [] Heart problems [] Epilepsy/Seizures [] Asthma or Hay fever [] Chemo/Radiation therag [] Diabetes/abnormal blood	een treated for or told that you have: [] Anemia [] AIDS [] Arthritis [] Glaucoma [] Drug addiction [] Skin problems [] Blood Disorders oy [] Cancer/Tumor od sugar [] Kidney/Liver disease
If yes, Please explain: Please check if you have b [] Abnormal bleeding [] Hemophilia [] Blood transfusion [] Ulcers/Colitis [] Heart problems [] Epilepsy/Seizures [] Asthma or Hay fever	een treated for or told that you have: [] Anemia [] AIDS [] Arthritis [] Glaucoma [] Drug addiction [] Skin problems [] Blood Disorders Oy [] Cancer/Tumor

OCT - 7 2025

APPENDIX V

Do you have a history of allergies to any oral care products, personal care consumer products, or their ingredients?

If yes, please fi	ll explain:		
Do y List any p	you take any med prescription or ove	ications? If yes	s, please fill out following: edications which you are taking:
Name of Medication	Amount taken	How often	Reason
	1		
	D	ENTAL HIST	TORY
Name of your o	dentist:		Phone#:
He	ow often do you vi	sit your Dentis	t?
	Date of	of last visit:	
		WOMEN ON	LY
	Plea	se answer the fo	ollowing:
Ara vou r	vragnant? V	N If was	list due data
Are you p			list due date;;;
-	, 1	,	
also understand to responsibility to in	hat this information form this office of	n will be held in fany changes in	day is correct to the best of my knowledge n the strictest of confidence, and it is my n my medical status. I understand that my
participation on this s	tudy is voluntary a	nd that I termir	nate my participation in the study at any tin
-	Signature		Date

APPENDIX VI INITIAL SCREENING FORM

OCT	1	7	2025
-----	---	---	------

PAPROVED"

Subje	ct Number:	Subject Initials:	_ Gender [] M	[] F A g	ge:	
3. 4.	1. Signed Inform 2. Male and fem All maxillary anterio without the presence Average VITA Exter or darker for 6 maxill	ned Consent Form hale subjects, aged 18-70, in r teeth must be present; of crowns/restorations haded BleachedGuide 3D-Ma	clusive aster shade of 17	YES_	YES N YES N NO NO YES N	OV
If ansv	ver to any of questions lestion 14 below comple	1-5 is No, subject is ineligible eted. If subject is eligible, co	e for study. Subjections	ct should s 6-13.	d be dismiss	ed
6.7.	Obvious signs of perior any condition that exclusionary from the 8. Five or more	odontal disease, rampant ca the dental examiner consider	aries, ers mediate care.		_ NO NO YESN	
	10. Self-reported	pregnant and/or lactating w	omen.		YES N	1 O
11.12.13.	hydrogen peroxide, p products, or their ing Restorations on the te with scoring procedu Have used profession and/or had a dental pr	eeth to be scored which may	n one (1) year ntal cleaning)	YES_	NO NO	
If anso	wer to any of question ssed and Question 14	ns 6-13 is YES, subject is i completed.	neligible for stud	y. Subj	ect should	be
	14. IS SUBJECT	ELIGIBLE FOR ENTRY I	NTO THE STUD	Υ?	YES N	10
SIGN	ATURE EXAMINING	G DENTIST	DATE:			

U.S.IRA

